- 28) The day before the first dose (12–24 hours prior to the planned infusion start time), eligible subjects will self-administer oral prednisone premedication based on body weight.
- 29) Study drug (or placebo) will be administered as a single peripheral IV infusion over ≥ 4 hours on Day 1, over ≥ 3 hours on Day 29, and over ≥ 2 hours for subsequent infusions (Days 57, 85, 113, and 141). Refer to the Pharmacy Manual for detailed instructions on preparation, administration, and infusion rate schedule requirements.
- 30) If a new or worsening symptom (or clinically significant finding) is observed or reported, the Investigator or designee will perform a symptom-directed physical examination. Symptom-directed physical examinations will be performed as needed and may be performed predose, during infusion, and/or postdose (including for possible IRRs).
- 31) All AE, including Adverse Events of Special Interest (AESI) and SAE, will be captured beginning from the start of the first infusion. Serious adverse events occurring between the time of consent and the start of the first study drug infusion will be reported only if they are assessed to be related to study procedures. For subjects participating in the OLE period, AE will be assessed and recorded in the CRF of the AK002-014 treatment period database up until the start of the first open-label infusion during the Day 176 visit and recorded in the CRF of the AK002-014 OLE period database beginning from the start of the first open-label infusion during the Day 176 visit.
- 32) ET visits should be conducted 28 (± 3) days after the last dose of study drug or prior to this, if necessary, to ensure compliance with the visit. If a subject discontinues the study > 28 days after the last dose of study drug, the ET visit should be conducted as soon as possible. If the subject is terminated after Day 29 and before Day 169, the ET visit will be performed 28 (± 3) days after last dose and the ET visit will follow the Day 169 assessment schedule (including EGD with biopsy collection). If the subject is not participating in the OLE period and the ET visit occurs after Day 169, the Day 197 assessment schedule should be followed for the ET visit. See [Table 5](#) OLE Period Schedule of Events for OLE period ET after Day 176.

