- 33) If absolute lymphocyte and/or eosinophil counts do not recover (to normal range or baseline levels) by Day 197 (or ET), extended follow-up visits are required every 28 (± 3) days) to monitor blood counts until they recover. Extended follow-up visits consist of blood collection for CBC with differential and collection of AESI and SAE.
- 34) After completion of the Day 169 visit, the Investigator will evaluate whether the subject is eligible for the OLE period. If the subject is eligible, the subject will be given the option to participate in the OLE period beginning approximately 1 week after the Day 169 visit. Approximately 1 week after the Day 169 visit (on Day 176 ± 3 days), eligible subjects that choose to participate in the OLE period will begin following the OLE Schedule of Events (Table 5) and will receive the first open-label AK002 infusion. For subjects participating in the OLE period, AE and concomitant medications should be collected and recorded in the AK002-014 Treatment Period database up until the start of the first open-label infusion during the Day 176 visit. This includes prednisone premedication administered prior to the Day 176 visit of the OLE period, which should be recorded in the Concomitant Medications CRF of both the AK002-014 treatment period database and the AK002-014 OLE period database.
- 35) Sites should strive to conduct visits within a ± 3 day window, but visits conducted within ± 7 days are acceptable and are not considered deviations. Visits conducted ± 4 -7 days from the target visit date should be minimized as much as possible. Any visit conducted outside of the ± 3 day window should receive prior written approval from Allakos.

6. Criteria for Evaluation

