12.1 Screening Period

- 1) Obtain written informed consent.
- 2) Begin the collection of SAE related to any screening activities.
- 3) Collect demographics and medical history.
- 4) Add the subject in EDC to assign a PID.
- 5) Complete in Screening Visit Date eCRF by selecting “Initiate Visit.”
- 6) Activate electronic questionnaires (ePROs) and provide subject with ViedocMe username and PIN.
- 7) Train subject on daily completion of the DSQ, Solid Food Question (if applicable), and the EG/EoD PRO Questionnaire.
- 8) Have the subject complete the CCI questionnaire via ViedocMe using their personal electronic device while they are at the site. Remind the subject to begin completing the daily questionnaires after the last meal of the day.
- 9) Provide subject a stool collection kit and instruct them to return the stool sample to the site within 24 hours of collection (unless subject can provide sample while on site).
- 10) Perform Baseline Diet Assessment.
- 11) Record prior and concomitant medications.
- 12) Determine body weight and height.
- 13) Obtain vital signs before blood draws.
- 14) Perform a complete physical examination.
- 15) Obtain a 10-lead or 12-lead ECG before blood draw.

- 16) Collect the following samples for the central laboratory:
 - a) Serum pregnancy test and FSH (for female subjects)
 - b) Serology
 - c) CBC with differential
 - d) Chemistry
 - e) Urinalysis
 - f) Blood for exploratory analysis
- 17) Perform a Screening/Baseline EGD with endoscopic severity grading per EREFS and biopsy collection per the study histology manual.
- 18) Obtain Histology Results Report from the Central Histology Reader, confirm intraepithelial eosinophilic infiltration is enough to qualify the subject for the study and that there are no exclusionary criteria found on the EGD.
- 19) Evaluate eligibility on an ongoing basis as the screening assessment results are obtained.

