12.2 The Day Before the First Infusion

- 1) Confirm eligibility.
- 2) Subject will self-administer oral prednisone premedication (dose based on body weight) 12–24 hours prior to the planned infusion start time. Ensure this is documented contemporaneously (e.g., subject emails the site when taking the premedication, subject texts the Study Coordinator when taking the premedication, etc.).

12.3 Day 1 – Dose 1

- 1) Pre-Infusion:
 - a) Confirm continued eligibility.
 - b) CCI to be self-administered by the subject via their personal electronic device.
 - c) Document any changes to health status.
 - d) Document any changes to concomitant medications including confirming and documenting the date and time the subject self-administered premedication.
 - e) Document any changes to baseline diet.
 - f) Determine body weight.
 - g) Collect vital signs.

- h) Perform symptom-directed physical exam, as needed.
 - i) Collect the following samples for the central laboratory:
 - Total Serum IgE
 - CBC with differential
 - Chemistry
 - Pharmacokinetics
 - Anti-drug antibodies
 - Urinalysis, if warranted in the opinion of the Investigator or Subinvestigator
 - j) Perform urine pregnancy test (if subject is of childbearing potential).
 - k) Enter the subject's PID and body weight in the IRT system to randomize the subject.
 - l) Once the subject has been randomized in the IRT system, the pharmacist will receive an email with PID, body weight, and kit number.
 - m) The study pharmacist will prepare study drug using the weight obtained at the visit. The final combined volume of the IV bag of study drug + 0.9% NaCl will be **120 mL**.

Note: **100 mL** of the calculated dose of study drug will be administered to the subject. The extra 20 mL is to be used to prime the IV infusion line during the preparation of the IV line at the bedside or to be left over in the infusion bag.
- 2) During the Infusion of Study Drug:
- a) Infuse 100 mL of study drug over at least 4 hours using an infusion pump per the instructions and infusion rate schedule in the Administration of Investigational Product section of the Pharmacy Manual. Record the start and stop times of the infusion including any times the infusion is interrupted.
 - b) Collect vital signs 15 (\pm 5) minutes after the start of infusion.
 - c) Perform symptom-directed physical exam, as needed.

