13.6.4 Assessment of Causality to Study Procedure

The Investigator should use their clinical judgment as well as the guidelines in Table 4 to assess the relationship between study procedure and AE. Assessment of Causality to Study Procedure should include causality to such items as EGD with biopsy or blood draw (as appropriate), or other.

Table 4 Adverse Event Relationship to Study Procedure

Relationship to Study Procedure	Comment
Related	There is clear evidence that the event is related to a study procedure.
Possible	The event cannot be explained by the subject's medical condition, concomitant therapy, or other causes, and there is a plausible temporal relationship between the event and a study procedure.
Unlikely/Remote	An event for which an alternative explanation is more likely (e.g., concomitant medications or ongoing medical conditions) or the temporal relationship to any study procedure suggests that a causal relationship is unlikely (For reporting purposes, Unlikely/Remote will be grouped together with Not Related).
Not Related	The event can be readily explained by the subject's underlying medical condition, concomitant therapy, or other causes, and therefore, the Investigator believes no relationship exists between the event and a study procedure.

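### AE recording starts at the first infusion, 12–24 hours after the required prednisone, so early premedication events go unrecorded, while the matching interval before the OLE counts as double-blind

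*Protocol*

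**What the plan says.** **Premedication.** Protocol 12.2 gives the instruction for the day before Day 1: "Subject will self-administer oral prednisone premedication (dose based on body weight) 12–24 hours prior to the planned infusion start time". It applies to all subjects in all three arms.

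**Start of AE recording.** Table 1 note 31 states: "All AE, including Adverse Events of Special Interest (AESI) and SAE, will be captured beginning from the start of the first infusion". Sections 13.1 and 13.7.1 set the same start, and the SAP repeats note 31 under its own Table 1.

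**Exception for SAEs.** Under note 31, SAEs between consent and the first infusion "will be reported only if they are assessed to be related to study procedures". Section 12.1 is wider: "Begin the collection of SAE related to any screening activities". Sections 13.2 and 13.7.1 refer to screening procedures. On what counts as a procedure, 13.6.4 says: "Assessment of Causality to Study Procedure should include causality to such items as EGD with biopsy or blood draw (as appropriate), or other".

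**Day 1 before the infusion.** Section 12.3 asks the site to "Document any changes to health status" and to confirm the date and time of the prednisone.

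**OLE entrants.** Prednisone is taken again 12–24 hours before the first open-label infusion (19.12.1). Note 34 says that "AE and concomitant medications should be collected and recorded in the AK002-014 Treatment Period database up until the start of the first open-label infusion". The TEAE definitions (Protocol 15.8; SAP 4.1, Table 2) have a start date and no end date. Safety data after Day 169 are analysed at the final lock (Protocol 16.4; SAP 5.6).

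**The concern.** Prednisone is part of the regimen that every subject must follow, adolescents included. A safety record that opens only after it has been taken cannot show what it does in its first 12–24 hours. Someone who reacts and is then not infused also falls outside the Safety population (SAP 6.1.1), so that reaction appears in no TEAE table.

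The second prednisone exposure is handled the opposite way. The same drug, at the same interval before an infusion, now falls inside the recorded period, and its early events are added to the randomised arm's TEAEs. Only OLE entrants can contribute them. Entry depends on the subject's choice and on the investigator's view of tolerability (19.12.3.2), and either could differ by arm. The documents give no reason for treating the two exposures differently.

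**Working it through.** The plan states no figure for this point. The check is a comparison of windows, followed by an illustration of size.

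**1. First exposure.**
- Prednisone: 12–24 hours before infusion start (12.2).
- AE recording opens: at infusion start (note 31, 13.1, 13.7.1).
- Gap: 12–24 hours per subject. For about 300 subjects (7.1), 300 × 0.5 to 300 × 1 = 150 to 300 subject-days.
- Non-serious onset in the gap: no AE record. A note of changed health status in the source carries no required severity, causality or outcome.
- Onset after infusion start: collected.

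**2. Is a prednisone-related SAE in the gap reportable?**
- For: Table 1 puts the prednisone row in the screening column, 12.1 covers any screening activity, and the list in 13.6.4 is open-ended.
- Against: note 31, 13.2 and 13.7.1 speak of procedures, and 13.6.4 names endoscopy and blood draw but not premedication. Section 9.1 limits study drug to AK002 and placebo, so prednisone is not study drug either.
- Both readings are possible, so sites may differ.

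**3. Can the first gap bias the arms?** Randomisation takes place on Day 1 (10.2; 12.3), after the prednisone. Events before it cannot depend on the assigned arm.

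**4. Second exposure.** The treatment-period database stays open until the first open-label infusion, and the TEAE definition has no end date. An event that begins in those 12–24 hours is therefore a TEAE under the randomised arm. Onset after the first open-label infusion goes to the OLE database.

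**5. Size, on assumed rates.** The documents give no rate for events with onset in such a window. I assume 1%, 5% and 10%.
- Unrecorded before Day 1 = 300 × rate = 3, 15 or 30 events (1, 5 or 10 per 100-subject arm).
- OLE interval = 300 × entry share × rate. Entry requires completing Day 169, and the plan allows for 14% dropout (15.2), so I take an assumed 70% up to 100% − 14% = 86%. Lowest: 300 × 0.70 × 0.01 = 2.1. Highest: 300 × 0.86 × 0.10 = 25.8.
- Arm difference in the share of subjects with such an event = entry difference × rate. With an assumed entry difference of 0–10 points and a rate of up to 10%: 0 to 0.10 × 0.10 = 0.01, that is 0 to 1 percentage point.
- The line for at least one TEAE counts each subject once. It rises by less than entry share × rate, because a subject who already has a TEAE adds nothing.

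**The case against.** The strongest reply is that little is lost and nothing is biased. A prednisone-related SAE can be read as already covered. Before the Day 1 infusion the site records health status, vital signs, blood count and chemistry, and examines symptoms as needed. The safety objective concerns AK002, and no formal inference is planned for safety. For the OLE interval, the rule is explicit and stated consistently. No open-label AK002 has yet been given, the event falls within 8 weeks of the last blinded dose, and the prednisone is entered in both databases, so affected events can be traced.

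Much of this stands, and it rules out several stronger readings that a reader might infer:
- *All prednisone harms are missed.* Only non-serious events with onset in the gap, and SAEs not judged procedure-related, are at risk. Later onset is recorded.
- *All reactions to the OLE prednisone are charged to the randomised arm.* Only those that begin before the first open-label infusion are.
- *Overall TEAE incidence rises by OLE entry share times reaction rate.* Incidence counts subjects once, and the documents supply no rate.
- *These events belong in the OLE tables.* That would put events in former placebo subjects, who have never received AK002, under open-label AK002.

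The reply does not remove the gap for non-serious events, since a source note on health status is not an AE record. Nor does it settle the SAE wording, which a site must be able to apply without choosing between readings.

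**Conclusion.** The point holds as a low-cost improvement to safety capture, not as a threat to the comparison of AK002 with placebo. The missing 12–24 hours understate the absolute harms of the regimen as given: about 3–30 unrecorded events in 300 subjects if 1–10% have one. SAE coverage in that window is ambiguous and should be settled by wording.

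The OLE interval adds perhaps 2–26 events to the double-blind TEAEs on the assumed rates and entry shares. The frequency of these events differs between arms only if OLE entry does, and then by no more than about 1 percentage point on the assumptions shown. All these sizes rest on assumed rates. The two windows and their opposite handling follow from the text alone.

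**What to change.** **Protocol.** In Table 1 note 31 and in 12.1, 13.1, 13.2 and 13.7.1, start AE and SAE collection at the prednisone intake before Day 1. Use one wording for the SAE exception throughout, and state in it, and in 13.6.4, that premedication is covered. Align the copy of note 31 in the SAP.

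**SAP, first exposure.** List events with onset before infusion start separately from TEAEs. Both TEAE definitions work by calendar date, so an event on the morning of Day 1 would otherwise count as treatment-emergent. The rule needs an onset time or a before-infusion tick box.

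**SAP, OLE exposure.** Flag events that begin between the OLE prednisone and the first open-label infusion and report them separately. Do not move them to the OLE.

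**Cost.** Amendment wording, about one extra day of AE recording per subject, and one date rule in the eCRF and analysis datasets. The prednisone date and time are already documented on Day 1, and the OLE dose is already entered in both databases.

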6.1 Safety Endpoints

The safety and tolerability of AK002 will be assessed by determining the following:

- Physical examination (Section 11.3.5, 11.3.6)
- Changes in vital signs (Section 11.3.4)
- Changes in Hematology (Section 11.2.8 and Section 11.4.1)
- Changes in Blood chemistry (Section 11.4.2)
- Changes in Urinalysis (Section 11.4.3)
- Anti-drug antibodies (Section 11.4.7)
- Treatment-emergent adverse events (Section 13) include severity, withdrawals due to AE, and other safety parameters.
- Changes in concomitant medications beginning on or after the first infusion of study drug (Section 11.3.1)

6.2 Pharmacokinetic Endpoints

Blood (serum) will be collected for assessment of AK002 concentrations using a validated enzyme-linked immunosorbent assay (ELISA) method. Pharmacokinetic blood samples will be obtained on Days 1, 8, 15, 29, 57, 85, 113, 141, 169, and 197 (or ET). On dosing days (Days 1, 29, 57, 85, 113, and 141), blood for PK will be collected predose.

Blood (serum) will be collected for assessment of AK002 ADA using a validated assay method. ADA blood samples will be obtained predose on Days 1, 29, 57, 85, 113, and 141, on Day 197 (or ET), and in the event of a suspected immunogenicity-related AE.

6.3 Efficacy Endpoints

6.3.1 Co-Primary Efficacy Endpoints

- 1) The proportion of subjects who achieve a peak esophageal intraepithelial count of ≤ 6 eosinophils/hpf at Week 24.
- 2) Mean change in DSQ score from baseline to Weeks 23–24.

6.3.2 Secondary Efficacy Endpoints

To further evaluate the efficacy of AK002 in adult and adolescent subjects with active EoE when compared to placebo as measured by:

- 1) Percent change in peak esophageal intraepithelial eosinophil count at Week 24.
- 2) Proportion of subjects achieving peak esophageal intraepithelial eosinophil count of ≤ 1 eosinophil/hpf at Week 24.
- 3) Proportion of subjects achieving peak esophageal intraepithelial eosinophil count of < 15 eosinophils/hpf at Week 24.
- 4) Proportion of treatment responders when a responder is a subject achieving $> 30\%$ reduction in symptoms (DSQ) at Weeks 23–24 and achieving a peak intraepithelial eosinophilic count of ≤ 6 eosinophils/hpf at Week 24.
- 5) Proportion of subjects with $> 50\%$ reduction in DSQ score from Baseline to Weeks 23–24.
- 6) Percent change in DSQ score from Baseline to Weeks 23–24.
- 7) Change in biweekly mean DSQ over time.
- 8) Change in EoE Reference Score for Endoscopic Abnormalities from Baseline to Week 24.

6.4 Exploratory Endpoints

- 1) Change in CCI from Baseline to Week 24.
- 2) Change in CCI from Baseline to Week 24.
- 3) Change in CCI from Baseline to Week 24.

7. Subject Selection

7.1 Number of Subjects

Approximately 300 subjects with symptomatic EoE will be randomized 1:1:1 to receive 1 of 3 dose regimens in a double-blind fashion: placebo; the low dose regimen (1 mg/kg AK002 administered every 4 weeks for 6 doses); or the high dose regimen (1 mg/kg AK002 for the first dose followed by 3 mg/kg AK002 administered every 4 weeks for the 5 subsequent doses). Subjects who successfully complete the randomized, double-blind, placebo-controlled treatment period (including the Day 169 visit) may have the option to receive 6 doses of open-label AK002 through participation in the OLE period of the study.

7.2 Study Population

Male and female EoE subjects, aged ≥ 12 and ≤ 80 years who fulfill the eligibility criteria specified below.

7.3 Inclusion Criteria

Subjects with active EoE are eligible for enrollment into the study if all of the following criteria are met:

- 1) Male or female aged ≥ 12 and ≤ 80 years at the time of signing the ICF.
- 2) Confirmed diagnosis of EoE and intraepithelial eosinophilic infiltration of ≥ 15 eosinophils/hpf in 1 hpf from a biopsy collected during the Screening EGD without any other cause for the esophageal eosinophilia.
- 3) Baseline DSQ (biweekly mean DSQ) score of ≥ 12 from the last 2 weeks of screening (the 14 days prior to the first dose) per the validated algorithm in [Appendix 11](#).
- 4) History (by subject report) of an average of ≥ 2 episodes of dysphagia with intake of solid foods per week during the 4 weeks prior to screening.
- 5) Subjects must have failed or not be adequately controlled on standard of care treatments for EoE symptoms, which could include PPI, systemic or topical corticosteroids, and/or diet, among others.
- 6) If on an allowed treatment for EoE (per Section 8.2), stable dose for at least 4 weeks prior to screening and willingness to continue that dose for the study duration.
- 7) If subject is on preexisting dietary restrictions, willingness to maintain dietary restrictions throughout the study, as much as possible.
- 8) Able and willing to comply with all study procedures.
- 9) Female subjects must be either post-menopausal for at least 1 year with FSH level >30 mIU/mL at screening or surgically sterile (tubal ligation, hysterectomy, or bilateral oophorectomy) for at least 3 months, or if of childbearing potential, have a negative pregnancy test and either agree to use dual methods of contraception, have a partner who had a vasectomy, or agree to abstain from sexual activity from screening until the end of the study, or for 120 days following the last dose of study drug, whichever is longer.

Non-vasectomized male subjects with female partners of childbearing potential must agree to either abstain from sexual activity or agree to use a highly effective method of contraception from screening until the end of the study or for 120 days following the last dose of study drug, whichever is longer. All fertile men with female partners of childbearing potential should be instructed to contact the Investigator immediately if they suspect their partner might be pregnant at any time during study participation.

7.4 Exclusion Criteria

Subjects will be excluded from the study if they meet any of the following criteria:

- 1) Concomitant moderately or severely symptomatic EG and/or EoD*, defined as:
 - ≥ 30 eosinophils/hpf in 5 hpf in the stomach (EG) and/or ≥ 30 eosinophils/hpf in 3 hpf in the duodenum (EoD) without any other cause for eosinophilia as determined by central histology assessment of biopsies collected during the Screening EGD.

and

- EG/EoD PRO Questionnaire weekly average single symptom score of ≥ 3 during the last 2 weeks of screening for 1 of the following symptoms: abdominal pain, nausea, and/or diarrhea.
- * This exclusion criterion is only applicable to sites actively enrolling subjects in the AK002-016 study. If a site is *not* actively screening and enrolling subjects in the AK002-016 study, then this exclusion criterion is not applicable.
- 2) Causes of esophageal eosinophilia other than EoE or one the following: hypereosinophilic syndrome, eosinophilic granulomatosis with polyangiitis, or peripheral blood absolute eosinophil count >1500 eosinophils/ μL .
 - 3) History of inflammatory bowel disease, celiac disease, achalasia, and/or esophageal surgery.
 - 4) Any esophageal stricture unable to be passed with a standard diagnostic 9 mm to 10 mm upper endoscope or any critical esophageal stricture that requires dilation during screening.
 - 5) History of bleeding disorders or esophageal varices.
 - 6) History of malignancy, except carcinoma in situ, early stage prostate cancer, or non-melanoma skin cancers. However, cancers that have been in remission for more than 5 years and are considered cured can be enrolled (with the exception of breast cancer).

All history of malignancy (including diagnosis, dates, and compliance with cancer screening recommendations) must be documented and certified by the Investigator, along with the statement that in their clinical judgment the tissue eosinophilia is attributable to EGID, rather than recurrence of malignancy.

- 7) Active *Helicobacter pylori* infection (as determined by central histology staining of the biopsy collected during the Screening EGD), unless treated and confirmed to be negative prior to randomization and symptoms remain consistent.

- 8) Positive Ova and Parasite test at screening, seropositive for *Strongyloides stercoralis* at screening, and/or treatment for a clinically significant helminthic parasitic infection within 6 months of screening.
- 9) Seropositive for HIV or hepatitis at screening, except for vaccinated subjects or subjects with a history of hepatitis that has since resolved.
- 10) Prior exposure to AK002 or hypersensitivity to any constituent of AK002.
- 11) Change in dose of inhaled corticosteroids, nasal corticosteroids, PPI, and/or diet therapy within 4 weeks prior to screening.
- 12) Use of oral corticosteroids (swallowed topical or systemic corticosteroids) within 8 weeks prior to screening.
- 13) Use of any biologics or medications that may interfere with the study, such as immunosuppressive or immunomodulatory drugs including azathioprine, JAK inhibitors, 6-mercaptopurine, methotrexate, cyclosporine, tacrolimus, anti-TNF, anti-IL-4 receptor (e.g., dupilumab), anti-IL-5 (e.g., mepolizumab), anti-IL-5 receptor (e.g., benralizumab), anti-IL-13 (e.g., lebrikizumab), and anti-IgE (e.g., omalizumab), within 12 weeks prior to screening.
- 14) Participation in a concurrent interventional study with the last intervention occurring within 30 days prior to administration of study drug or 90 days or 5 half-lives, whichever is longer, for biologic products.
- 15) Vaccination with live attenuated vaccines ≤ 30 days prior to initiation of treatment in the study, during the treatment period, or vaccination expected ≤ 5 half-lives (≤ 4 months) following study drug administration (with the exception of a COVID-19 vaccine authorized by the FDA or other applicable regulatory agency).
- 16) Treatment with chemotherapy or radiotherapy in the preceding 6 months.
- 17) Presence of abnormal laboratory values considered by the Investigator to be clinically significant.
- 18) Any disease, condition (medical or surgical), or cardiac abnormality, which in the opinion of the Investigator, would place the subject at increased risk.
- 19) Known history of alcohol, drug, or other substance abuse or dependence.
- 20) Women who are pregnant, breastfeeding, or planning to become pregnant while participating in the study.
- 21) Any other reason that in the opinion of the Investigator or Medical Monitor makes the subject unsuitable for enrollment.

8. Prior and Concurrent Medications

Prior and concomitant medications (which include both prescribed and over-the-counter medications taken at any point beginning 30 days prior to the screening visit and until the end of study participation) will be recorded in the electronic Case Report Forms (eCRF). For subjects participating in the OLE period, concomitant medications should be recorded in the AK002-014 treatment period database up until the first open-label dose is administered during the Day 176 visit. This includes the prednisone premedication administered prior to the Day 176 visit in the OLE period, which should be recorded in the Concomitant Medications CRF of both the AK002-014 treatment period database and the AK002-014 OLE period database.

Subjects should be advised against taking any new medication or modifying the dose of existing medication, both prescribed and over the counter, without consulting the Investigator, unless the new medication or change in dose is required for emergency use. Immediately prior to the first infusion, study site personnel should ensure that the subject continues to meet the inclusion criteria and none of the exclusion criteria including no use of prohibited medications. All medications taken for the 30 days before screening and during participation in this study must be documented on the eCRF. All medications used to treat IRR or AE must also be documented.

